Title: Efficacy of Low-Level Light Therapy in Combination with Topical Non-Steroidal Immunosuppressants for the Treatment of Dry Eye Disease: A Multicenter, Randomized, Single-Masked, Active-Controlled Trial.

NCT number: ID not yet assigned.

Date: 10/13/2025.

Study protocol

This was a randomized, single-masked, active-controlled trial conducted at Centro Oculistico Borroni (Varese, Gallarate, Italy) and Biomeeting Day Surgery center (Calabria, Reggio Calabria, Italy) between May, 2024 and June 2025. The study protocol was approved by the institutional review board of the Riga Stradiņu University (nr.29/20092016) and adhered to the Declaration of Helsinki. Written informed consent was obtained from all participants prior to enrollment. The study was registered at ClinicalTrials.gov (identifier, XXX) and follows the Consolidated Standards of Reporting Trials (CONSORT) guidelines [26].

Participants

Participants eligible for inclusion were adults ≥ 25 years old with a self-reported history DED. To be enrolled in the study, participants were required to meet the following inclusion criteria in at least one eye: (1) Ocular Surface Disease Index (OSDI) score > 13 ; (2) non-invasive tear film break-up time (NIBUT) < 10 seconds; and (3) tear meniscus height < 0.25 mm. Participants were excluded if they met any of the following conditions: (1) structural abnormalities of the eyelids; (2) active blepharitis; (3) corneal disorders that could interfere with study assessments, such as active corneal infections or corneal dystrophies; (4) active ocular allergy; (5) history of procedures for DED treatment within the previous 12 months, such as eyelid exfoliation, thermal eyelid therapies, light therapies, or quantum molecular resonance (QMR); (6) history of intraocular or laser ocular surgery within the past 5 years; (7) current use of topical antibiotics or anti-inflammatory agents; (8) diagnosis of systemic autoimmune disease; (9) contact lens wear; (10) pregnancy or lactation; and (11) inability to understand or provide informed consent. Prior use of tear substitutes was allowed, and there was a 4-week washout period after enrollment.

Randomization, intervention, and masking

Eligible participants were randomized in a 1:1:1:1 ratio to receive either topical CsA 0.1% (CsA group), topical Tacrolimus 0.1% (Tacrolimus group), LLLT combined with topical CsA 0.1% (LLLT–CsA group), or LLLT combined with topical Tacrolimus 0.1% (LLLT–Tacrolimus group). A random allocation sequence was generated using Randomizer.app (PWA Labs Inc., CA, USA) by an ophthalmologist who was not otherwise involved in the study. The same individual was responsible for performing the LLLT procedure and providing CsA 0.1% or Tacrolimus 0.1% according to group allocation. Treatment allocation was concealed from the ophthalmologists and optometrists involved in the study until the conclusion of data analysis.

- Photobiomodulation: LLLT was administered using the eye-light[®] device (Espansione Group, Bologna, Italy), which employs Light ModulationTM technology. The treatment was delivered with a wavelength of 625 nm and a radiance of 35 mW/cm², resulting in a total energy dose of approximately 32 J/cm² applied to the facial and eyelid regions with eyes

closed. Three 15-minute sessions were performed at weekly intervals starting at the baseline visit. The same protocol was repeated at the 6-month follow-up, following evaluation of the outcome measures.

- Topical CsA and Tacrolimus preparation: CsA 0.1% and Tacrolimus 0.1% were prepared as sterile aqueous microemulsions. The formulation excluded ethanol and preservatives, using the the most functional and minimal number of excipients to minimize adverse events: ethoxylated hydrogenated castor oil, polysorbate 80, sodium chloride, sodium hyaluronate, phosphate buffer (pH: 6.8 - 7.2), and water for injections. A concentrated 10 mg/mL emulsion was first prepared in a biological safety cabinet, then mixed under sterile cleanroom conditions with a buffered base solution containing the other excipients. Final sterilization was performed using 0.22 μ m filtration under a Grade A hood, followed by packaging in sterile dropper bottles. CsA 0.1% and Tacrolimus 0.1% were clear and odorless, thereby minimizing sensory differences for the participants. Moreover, the bottles were identical in both appearance and labeling, which helped ensure that patients remained masked to their treatment allocation. Patients were instructed to apply the medications every 12 hours.

Assessment of the outcome measures

The study design is shown in Fig. 1. Patients were assessed at screening, baseline (day 1), and 2 follow-up visits: 6 months (24 ± 2.5 weeks) and 12 months (48 ± 2.2 weeks). The primary efficacy outcome measure was the change from baseline at months 6 and 12 in OSDI score. The OSDI questionnaire was performed during each follow-up visit as part of the clinical consultation. The secondary efficacy outcome measures were the change from baseline at months 6 and 12 in tear film stability and tear volume, assessed using the Sirius device (CSO, Florence, Italy). Tear film stability was automatically assessed through non-invasive tear film break-up time (NIBUT) by projecting Placido rings from the Sirius device onto the corneal surface. The time interval between the last blink and the initial distortion of the ring pattern was defined as first NIBUT. For statistical analysis the average of 3 consecutive measurements was calculated for each participant. Tear volume was evaluated with TMH using the tear film scanning function of the Sirius device. Measurements were performed below the corneal vertex at the 6 o'clock position using the device's built-in software calliper tool. The Sirius device was located in the same examination room throughout the study period, with controlled temperature and humidity conditions. Outcome measures were conducted under scotopic conditions, at the same time of day to minimize diurnal variability of TMH. All measurements were performed by a well-trained optometrist.

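### The allocation sequence came from someone described as having no other role, who also gave the LLLT and supplied the drops; the independence claim fails and the concealment claim must be narrowed

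*Protocol*

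**What the plan says.** Three consecutive sentences of the Protocol, under Randomization, intervention, and masking, bear on this point.

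- The list was produced with a web tool: "A random allocation sequence was generated using Randomizer.app", and this was done "by an ophthalmologist who was not otherwise involved in the study".
- On who delivered treatment, the Protocol then says: "The same individual was responsible for performing the LLLT procedure and providing CsA 0.1% or Tacrolimus 0.1% according to group allocation".
- On who was kept unaware of the arm, it goes on: "Treatment allocation was concealed from the ophthalmologists and optometrists involved in the study until the conclusion of data analysis".

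The same section gives the ratio ("Eligible participants were randomized in a 1:1:1:1 ratio") and the timing of the light treatment: "Three 15-minute sessions were performed at weekly intervals starting at the baseline visit", with the course repeated at 6 months. Under Assessment of the outcome measures, the Protocol adds "All measurements were performed by a well-trained optometrist" and, for the primary outcome, "The OSDI questionnaire was performed during each follow-up visit as part of the clinical consultation". The title and the Study protocol section call the trial single-masked. The SAP says nothing about sequence generation or concealment.

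**The concern.** Randomization protects a comparison when nobody who knows the next assignment can affect who receives it. A reader told that an uninvolved person made the list will take that protection as given. Here the text withdraws it one sentence later, because delivering the light treatment and supplying study drops in a four-arm treatment trial is involvement.

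What is at stake is what the trial may claim. If one clinician made the list and treated from it, and nothing is said about how the next assignment was kept from that person, the report cannot describe allocation by an independent party. It also cannot say that every study ophthalmologist was unaware of allocation. The primary outcome is a patient questionnaire, and the Protocol does not name who conducts the consultation in which it is completed. Readers will therefore lean on these statements when judging freedom from bias.

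**Working it through.** The Protocol gives no figure for this point, so the check is a side-by-side reading.

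**Step 1: who is the same individual?** The preceding sentence names one person, the ophthalmologist who generated the sequence. There is no other candidate.

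**Step 2: do the sentences agree?**

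| Statement | What it requires of this person |
|---|---|
| Sequence generation | No other part in the trial |
| Treatment delivery | Gives LLLT and supplies the drops, acting on the assigned arm |
| Concealment | Being an ophthalmologist involved in the study, does not know allocation until analysis is complete |

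The second row contradicts the first. It also contradicts the third, because a person cannot treat by arm without knowing the arm. The third row can hold only if it means the other ophthalmologists and the optometrists.

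**Step 3: is there a safeguard elsewhere?** I looked in both documents for a central service, sealed envelopes, a separate holder of the list, or a rule fixing the assignment before treatment contact. None is described. Block size, stratification and access to the list are also not stated. Nor is it said who enrolled participants or judged eligibility, or how one individual covered two centres.

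**Step 4: where could knowledge of the list matter?** In the two LLLT arms the treatment begins at baseline. There are three sessions then and three more after the 6-month assessment, so 3 + 3 = 6 contacts per participant. For the two drops-only arms, the text does not say when or how bottles were handed over, so contact at baseline cannot be assumed.

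**Step 5: how many assignments are affected?** Taken literally, all of them, in all four arms. The SAP plans 24 eyes per group, which is 4 × 24 = 96 eyes. The Protocol randomizes participants, and the documents do not say how many eyes each contributes. If it is one eye each, the plan means 96 assignments; if two, 96 / 2 = 48. The range of 48 to 96 rests on that assumption. It counts the assignments exposed and does not measure bias.

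**The case against.** The best reply is that the dual role is disclosed openly. Read together, the first two sentences may mean an ophthalmologist with no role beyond making the list and delivering treatment, and the third sentence then refers to everyone else. On that reading this is loose drafting. That may be what was intended, but the Protocol does not say it, and the phrase as printed claims an independence that the next sentence removes.

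The rest of the reply limits how far the point can go, and most of it stands:

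- A reader might infer that this clinician chose who entered the trial or steered borderline patients. The documents do not support that. Only eligible participants were randomized, screening is listed separately from baseline, a 4-week washout follows enrolment, and an optometrist took the measurements, which include two of the entry criteria. Nothing says the list holder screened, enrolled or judged eligibility. What remains is possible influence on the order in which enrolled participants took assignments.
- A reader might infer that outcome assessors were unmasked. The text says the opposite for optometrists, and leaves open only who ran the questionnaire consultation.
- A reader might treat an unmasked supplier of the drops as a breach of masking. It is compatible with a single-masked design in which identical bottles and clear, odorless drops mask the patient to the drug. Differing instructions by arm would be speculation, since one dosing interval is stated for both drugs.
- It would be too strong to say that nothing can be done in analysis. Baseline balance can be inspected and measured baseline values adjusted for, although unmeasured differences would remain.
- The absence of a described safeguard does not prove that none existed.

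**Conclusion.** The point holds as a contradiction about the independence of allocation, with an undescribed concealment mechanism behind it. As written, the sequence generator was an unmasked treating clinician, and the concealment sentence cannot extend to that person. I hold this with high confidence, since it rests only on adjacent sentences and on the natural reading of who the same individual is.

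The consequence for bias is less certain. That this person knew upcoming assignments is a direct inference from having made the list, treated from it, and no barrier being described. That the knowledge altered the order of assignment is an open risk and not a demonstrated event. The documents give no basis for a magnitude. The finding changes what the trial can claim about concealment; it does not establish that any between-group comparison is biased.

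**What to change.** The Protocol reports conduct between May 2024 and June 2025 and is dated 10/13/2025, so roles cannot be separated for participants already treated. For them, correct the description:

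1. Remove the claim of no other involvement from "by an ophthalmologist who was not otherwise involved in the study".
2. State that one unmasked ophthalmologist generated the sequence, performed LLLT and provided the drops, and say how this worked across the two centres.
3. Limit the concealment and masking statement to the enrolling, measuring and analysing staff it truly covers, and say who conducted the consultation in which OSDI was completed.
4. State who enrolled participants, who held the list, and when each assignment was fixed relative to eligibility, baseline values and first treatment contact.
5. Do not claim allocation by an independent person unless a real safeguard can be documented. If one existed, describing it largely settles the open risk.

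For any further enrolment, have someone who does not treat participants hold the list and release each assignment only after eligibility and baseline values are recorded. The documents do not name a statistician or a separate compounding unit, so that role would have to be assigned, and its holder must be reachable on baseline days.

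For the completed trial the cost is a few sentences and a less favourable concealment statement. No new data are needed and no treatment rule changes.

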Title: Efficacy of Low-Level Light Therapy in Combination with Topical Non-Steroidal Immunosuppressants for the Treatment of Dry Eye Disease: A Multicenter, Randomized, Single-Masked, Active-Controlled Trial.

NCT number: ID not yet assigned.

Date: 10/13/2025.

Statistical analysis

Statistical analyses were conducted with SPSS statistics software, version 25.0 (IBM Corp., Armonk, NY, USA). The sample size was estimated using the GRANMO calculator, version 8.0 (Registre Gironí del Cor, Barcelona, Spain). It was calculated based on assumed mean difference in OSDI scores between groups at 6 months after the intervention onset, with a mean value of -8.05 ± 2.78 points (Range: -0.75 to -12.74). This assumed difference were based on the findings of a pilot study with 20 eyes of 10 patients in each group. With these assumptions, a sample size of 24 eyes per group would yield a power $> 80\%$ and a statistically significant paired difference of 95% confidence. A 5% lost to follow-up was considered when calculating sample size.

The Kolmogorov-Smirnov test confirmed that the outcome measures met the normality criteria, allowing for the application of parametric tests. A repeated measures ANOVA with Bonferroni-adjusted post hoc tests was conducted to assess intra-group changes. For each group, the change (Δ) was calculated for the intervals between baseline and month 6 ($M6$), baseline and month 12 ($M12$), and month 6 to month 12 ($M6 \rightarrow M12$), using the following formulas:

$$\Delta_{M6} = M6 - \text{Baseline} \quad \Delta_{M12} = M12 - \text{Baseline} \quad \Delta_{M6 \rightarrow M12} = M12 - M6$$

A one-way ANOVA with Bonferroni-adjusted post hoc tests was also performed to compare inter-group differences. The difference between the changes (D_Δ) observed within each group over the mentioned intervals was computed for each pair of groups, using the following formulas:

$$D_{\Delta M6} = \Delta_{M6}^{(x)} - \Delta_{M6}^{(y)} \quad D_{\Delta M12} = \Delta_{M12}^{(x)} - \Delta_{M12}^{(y)} \quad D_{\Delta M6 \rightarrow M12} = \Delta_{M6 \rightarrow M12}^{(x)} - \Delta_{M6 \rightarrow M12}^{(y)}$$

For all $x \neq y \rightarrow x, y \in \{CsA, Tacrolimus, LLLT-CsA, and LLLT-Tacrolimus groups\}$

Categorical variables were compared using the Chi-squared test (χ^2). Statistical significance and clinical relevance were evaluated. Statistical significance was defined as a P -value less than 0.05. Clinical relevance was estimated using partial eta squared (η_p^2) for ANOVAs, Cohen's d_z for within-group comparisons, and Cohen's d_s for between-group comparisons in Bonferroni-adjusted post hoc tests. According to Cohen's benchmarks, effect sizes were classified as small ($\eta_p^2 < 0.06$; $d_z = d_s < 0.5$), moderate ($\eta_p^2 \geq 0.06$ and < 0.14 ; $d_z = d_s \geq 0.50$ and < 0.8), and large ($\eta_p^2 \geq 0.14$; $d_z = d_s \geq 0.80$).

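### The change-score ANOVA drops participants lost before month 12 and ignores their month-6 OSDI, so symptom-related loss that differs by arm would bias the month-12 contrast

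*SAP*

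**What the plan says.** The Protocol (Assessment of the outcome measures) sets the primary endpoint: "The primary efficacy outcome measure was the change from baseline at months 6 and 12 in OSDI score". There are two post-baseline visits.

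The SAP (Statistical analysis) names two analyses:

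- Within arms: "A repeated measures ANOVA with Bonferroni-adjusted post hoc tests was conducted to assess intra-group changes".
- Between arms: "A one-way ANOVA with Bonferroni-adjusted post hoc tests was also performed to compare inter-group differences". This is applied to three intervals (baseline to month 6, baseline to month 12, month 6 to month 12) for every pair of the four arms.

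Loss is mentioned once: "A 5% lost to follow-up was considered when calculating sample size". Neither document defines an analysis set, states that participants are analysed in the arm allocated, gives a missing-data method or includes a sensitivity analysis.

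On the light-therapy course, the Protocol (Randomization, intervention, and masking) adds: "The same protocol was repeated at the 6-month follow-up, following evaluation of the outcome measures". Only two of the four arms have this course. Neither document says how the analysis treats a participant who did not receive it.

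**The concern.** With no missing-data method stated, the two procedures handle loss by deletion. A standard repeated measures ANOVA over baseline, month 6 and month 12 excludes anyone missing a visit. A one-way ANOVA of change excludes anyone missing either end of that interval. Two things follow.

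First, the within-arm and between-arm results, and the three intervals, can come from different participants. The SAP's formulas make the month-12 change the sum of the month-6 change and the month-6-to-12 change. That identity need not hold for the reported means.

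Second, a participant seen at month 6 and lost before month 12 contributes nothing to the month-12 contrast, although the month-6 score shows how that participant was doing. If those with poor month-6 symptoms leave more often, completers look better than the randomized arm. If this happens more in one arm than another, the primary month-12 comparison is shifted.

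**Working it through.** **Inputs from the documents.** 24 eyes per group, 5% loss, assumed difference -8.05, and ± 2.78 (not labelled; it may be an SD). The SAP states no bias or missing-data figure to reproduce. Its 24 does not follow from -8.05 and 2.78: the two-sample normal formula, 2 × 2.78² × (1.96 + 0.84)² / 8.05² = 1.9, gives 2 per group, or 3 after 5% loss. That is a separate matter and does not bear on this point.

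**Assumptions, not in the documents.** OSDI SD 8 to 12, between-visit correlation 0.5 to 0.7, unequal loss of 15 to 20% in one arm, and loss that rises with poor month-6 change. The calculation takes 24 participants per arm, whereas the SAP counts eyes.

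**Step 1: who enters each analysis.** Suppose each follow-up visit is missed independently with probability 5%.

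- Month-6 change: 24 × 0.95 = 22.8.
- Month-12 change: 24 × 0.95 = 22.8, not the same people.
- Month-6-to-12 change and repeated measures ANOVA: 24 × 0.95² = 24 × 0.9025 = 21.7, a loss of 9.75%.

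At 10% the figures are 21.6 and 19.4; at 15%, 20.4 and 17.3.

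**Step 2: bias in general.** In one arm, completer mean minus full mean = (share lost) × (stayer mean minus leaver mean). The bias of the contrast is the difference of this quantity between arms. Take a stayer-leaver gap of 2.78 to 8.05 points, chosen only for scale:

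- 20% v 5%, same kind of leaver in both arms: (0.20 - 0.05) × gap = 0.42 to 1.21 points.
- 5% v 5%, same kind: 0.
- 5% v 5%, opposite kinds: (0.05 + 0.05) × gap = 0.28 to 0.81 points.

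**Step 3: bias when loss depends on month 6.** Two-arm trials were simulated with 24 per arm, a true difference of -8.05 at both visits, and month-12 loss logistic in the standardized month-6 change (slope 1.5). Poor responders leave, with more loss in the comparator arm.

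| Loss | Complete-case month-12 difference | Likelihood estimate using month 6 |
|---|---|---|
| 5% v 5% | no between-arm bias | -8.0 to -8.1 |
| 5% v 15% | -7.4 to -7.7 | -8.0 to -8.1 |
| 5% v 20% | -7.0 to -7.5 | -8.0 to -8.1 |

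The bias is therefore about 0.3 to 1.0 points across the unequal-loss settings. Here it understates the difference. With the heavier loss in the other arm it overstates it by the same amount, to about -8.05 - 0.3 = -8.35 up to -8.05 - 1.0 = -9.05. At equal 5% loss, each arm's own improvement is still overstated by 0.2 to 0.4 points.

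**Step 4: if 2.78 is the SD.** The bias scales with the SD: 0.3 × 2.78/8 = 0.10 and 1.0 × 2.78/12 = 0.23, so about 0.1 to 0.25 points.

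**Step 5: against sampling error.** The standard error of the contrast is SD × √(2(1 - correlation)) × √(2/24). It runs from 8 × √0.6 × 0.289 = 1.8 to 12 × 1 × 0.289 = 3.5. The largest bias is 1.0/3.5 = 0.29 standard errors.

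**The case against.** A reader might infer a stronger chain: missing month 6 means missing the second LLLT course in two arms only, so the month-12 comparison is biased by who stays. The documents do not support it.

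- The month-12 contrast is the one-way ANOVA of month 12 minus baseline and does not need month 6. A participant who misses month 6 but attends month 12 stays in it, possibly with incomplete LLLT. That is a question of analysing as randomized, not of selection. If 5 to 20% missed a course worth an assumed 2 to 8.05 points, the effect would shift by 0.05 × 2 = 0.1 to 0.20 × 8.05 = 1.6 points.
- Attendance at month 6 is not the same as re-treatment. The course is three weekly sessions starting after that visit's assessment, and the Protocol does not say whether a missed course could be rescheduled.
- The repeated measures ANOVA deletes by the same rule in all four arms.
- The simulation contains no missed month-6 visits and no missed courses, so it cannot size that chain.

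Other objections stand in part. At the SAP's own 5%, if loss is alike in every arm, the between-arm bias is nil. Unequal loss, the SD and the dropout slope are assumptions, and the bias is under 0.3 standard errors. Deletion is inferred from how the named procedures work, not stated. The documents are dated after the June 2025 end of the trial and report that normality was confirmed, so replacing the primary analysis now may be a post hoc change.

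None of this supplies the missing analysis set or missing-data method, or brings the month-6 data into the month-12 contrast.

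**Conclusion.** The point holds as a weakness of method with a modest, conditional effect. The stated analyses can rest on different participants and discard month-6 information. Under symptom-related loss that differs by arm, the month-12 OSDI contrast is biased by about 0.3 to 1.0 points (SD 8 to 12) or 0.1 to 0.25 points (SD 2.78), in either direction. It is unbiased when loss is equal and of the same kind.

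A reader might conclude that this trial's result is in fact biased. The documents cannot show that, because they report no loss by arm. The change should be made, but it is not critical to the trial's validity on the evidence available.

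**What to change.** 1. Estimate all three changes and every D_Δ as contrasts from one mixed model for repeated measures (SPSS MIXED). Use OSDI at baseline, month 6 and month 12, with arm, visit and arm-by-visit as fixed effects and unstructured covariance over visits. Add participant-level clustering if both eyes of a patient are analysed.
2. Include every randomized participant with any OSDI value, in the arm allocated, whatever LLLT or drops were received. This also settles the separate question of incomplete LLLT.
3. Keep the current ANOVAs as a completers analysis.
4. Report the number lost, and LLLT sessions received, by arm and visit.
5. If outcome data have already been examined, label the mixed model a post hoc change and show both results.

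Cost: SAP wording and one procedure in the software already used, with no new data. Standard errors may be about 1 to 5% larger under unequal loss. The model relies on loss being explained by observed OSDI; it does not remove bias from loss that depends on the unseen month-12 score.

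### Within-arm tests of change stand beside the between-arm comparison with no ranking, and they cannot separate treatment from non-treatment change

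*SAP*

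**What the plan says.** The SAP's Statistical analysis section has two strands. The first is within arm: "A repeated measures ANOVA with Bonferroni-adjusted post hoc tests was conducted to assess intra-group changes". The second is between arms: "A one-way ANOVA with Bonferroni-adjusted post hoc tests was also performed to compare inter-group differences", with the difference in change computed for every pair of groups over baseline to month 6, baseline to month 12, and month 6 to month 12. Both are judged at P < 0.05. Both receive effect-size grades under the label of clinical relevance: d_z within groups and d_s between groups. No sentence ranks the strands or calls the first descriptive. The sample-size paragraph starts from a difference between groups and ends with a paired difference.

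The Protocol's Participants section says "participants were required to meet the following inclusion criteria in at least one eye". The criteria are "Ocular Surface Disease Index (OSDI) score > 13", "non-invasive tear film break-up time (NIBUT) < 10 seconds" and a tear meniscus height below 0.25 mm. It adds that "there was a 4-week washout period after enrollment". Under Assessment of the outcome measures, "The primary efficacy outcome measure was the change from baseline at months 6 and 12 in OSDI score" and "The secondary efficacy outcome measures were the change from baseline at months 6 and 12 in tear film stability and tear volume"; these last two are measured by NIBUT and tear meniscus height. That section lists screening and baseline (day 1) as separate assessments. All four arms receive CsA or tacrolimus, with or without LLLT.

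**The concern.** Patients enter because symptoms are high, break-up time is short and the meniscus is low. The outcomes are later changes in those same measures. Without an untreated, vehicle or sham arm, nothing in the trial shows how far an arm would have moved on its own. Three non-treatment sources could each produce a change that looks like benefit:

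- regression to the mean after selection on a threshold;
- response to taking part;
- recovery from a baseline worsened by the washout.

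A within-arm test keeps all of this in its estimate. A randomised contrast removes whatever part is common to the arms.

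The title asks about LLLT in combination with the drops. Significant improvement inside an LLLT arm does not answer that, and neither does a significant result in one arm beside a non-significant result in another. With equal true change and 50% power per arm, two arms disagree on significance with probability 2 × 0.5 × 0.5 = 50%. Because the plan does not say which strand carries the efficacy claim, a report could rest on the wrong one.

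**Working it through.** **Inputs from the documents.** 24 eyes per group, treated here as 24 independent observations; three analysed visits (baseline, months 6 and 12); alpha 0.05, taken as two-sided; Bonferroni over the three visit pairs, 0.05/3 = 0.0167.

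**Assumptions, not in the documents.** Normal scores, equal test–retest correlation r of 0.5 to 0.85 between visits, position of the threshold in the source population, and zero treatment effect in all arms.

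**1. The plan's own figure.** The SAP gives no figure for within-arm drift. Its 24 per group does not follow from −8.05 ± 2.78: the paired formula gives (2.78 × (1.960 + 0.842) / 8.05)² = 0.94, that is, 1. That is a separate matter; 24 is used here only as n.

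**2. Qualifying value is also the baseline.** With a threshold c SDs from the source mean (positive is stricter), the expected apparent improvement is (1 − r) × φ(c) / (1 − Φ(c)) SD:

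- c = −1, r = 0.85: 0.15 × 0.288 = 0.04 SD
- c = 0, r = 0.7: 0.30 × 0.798 = 0.24 SD
- c = 0.5, r = 0.5: 0.50 × 1.141 = 0.57 SD

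Simulated share of arms with within-arm ANOVA p < 0.05 and no treatment effect (repeat runs agree within simulation error):

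| Threshold | r = 0.5 | r = 0.7 | r = 0.85 |
|---|---|---|---|
| 1 SD lenient | 10% | 8% | 7% |
| At the mean | 54% | 34% | 18% |
| 0.5 SD strict | 88% | 61% | 33% |

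The omnibus test has no direction. Counting only Bonferroni-adjusted improvement from baseline to month 6 (nominal 0.0167/2 = 0.83%), the share of arms is 1.5–2.7% if 90% of candidates pass the threshold, 4–11% if 70% pass, 9–34% if 50% pass and 18–71% if 30% pass.

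**3. Baseline re-measured after qualification.** With constant correlation over time, the threshold component disappears: within-arm ANOVA p < 0.05 in 5% of arms, and Bonferroni-adjusted improvement in 0.5–1.0% against 0.83%.

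**4. Non-treatment change common to all arms, baseline re-measured.** The paired test at 0.05/3 has critical t(23) = 2.582, and the noncentrality is d_z × √24:

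- d_z = 0.3: noncentrality 1.47, significant in 16% of arms
- d_z = 0.5: noncentrality 2.45, significant in 46% of arms

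Without Bonferroni these would be 29% and 65%, but the SAP does specify the adjustment. In outcome units, a common shift of 0.25 SD at r = 0.7 has d_z = 0.25 / √(2 × 0.3) = 0.32; the omnibus within-arm ANOVA is then significant in about 34% of arms.

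**5. What the d_z grade adds.** The smallest observed d_z that reaches significance at 0.05/3 is 2.582 / √24 = 0.53. The SAP's moderate band starts at 0.50. So at n = 24 every significant post hoc change is automatically graded moderate or large. The grade is no independent check on whether treatment caused the change.

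**6. Between-arm one-way ANOVA of change.** In the same simulations, p < 0.05 occurs in about 4–6% of trials, with either definition of baseline and with common shifts of 0.25 to 0.75 SD.

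**The case against.** The comparison that answers the question is already planned. The between-arm ANOVA covers every pair, including each LLLT arm against its drug-only counterpart, and it holds its error rate. The SAP describes the within-arm strand only as an assessment of intra-group change, and nothing says that differing significance across arms will be read as a comparison. Separate screening and baseline visits, with a washout after enrollment, suggest that baseline was re-measured, in which case threshold regression largely vanishes. Candidates with a self-reported history of dry eye may mostly pass the thresholds, which would also make it small. No document gives drift, retest or rebound data.

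Most of this stands, and it limits the size. A reader might infer that the plan has no valid test of LLLT; the SAP contradicts that. A reader might also take the middle simulation row as the expected result: 34% of arms, hence at least one of four arms in 1 − 0.66⁴ = 81% of trials. That requires the qualifying value to be the baseline and the threshold to sit at the source mean. The documents establish neither, and the visit sequence leans against the first. Nor can it be stated as fact that all three outcomes drift towards benefit.

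The objection does not supply a ranking. The within-arm tests still carry p-values and relevance grades, unlabelled, and re-measuring baseline does not remove participation response or recovery after washout.

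**Conclusion.** The point holds as a gap in hierarchy and interpretation. The within-arm tests cannot support an efficacy claim in this design, and the SAP does not say that they will not be used for one. The size cannot be fixed from the documents. It runs from about 7% to 88% of arms if the qualifying value is the baseline. If baseline was re-measured, it is 5% from thresholds alone, rising to 16% or 46% on the Bonferroni-adjusted paired test if a common non-treatment change of d_z 0.3 or 0.5 is present. Threshold regression and washout recovery need not both act in full: qualification before the washout weakens the first.

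The 4–6% for the between-arm test assumes that non-treatment change is common to the arms. The documents describe no sham LLLT, so a response to the light sessions themselves would not cancel in the LLLT contrasts. The change proposed here does not cure that limit. Because a valid randomised comparison of change is already in the plan, the correction is worth making but does not put the trial's main comparison in doubt.

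**What to change.** - Report within-arm mean change with 95% CI, labelled as description. Drop its p-values and d_z relevance grades as evidence of efficacy, and state that an interval excluding zero does not show a treatment effect.
- Base every efficacy statement on the between-arm contrasts of change already planned, adjusted for the baseline value. The adjustment handles chance baseline imbalance; it does not repair the within-arm tests.
- Name LLLT–CsA versus CsA and LLLT–Tacrolimus versus Tacrolimus as the contrasts that answer the title question.
- State that significance in one arm and not in another is not a comparison.
- State which visit's values determined eligibility and whether baseline was measured again after the washout.

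The cost is SAP wording and a baseline term in the between-arm model, with no new data. The documents are written in the past tense, so this may mean relabelling and a short re-analysis. The sponsor gives up the claim of significant improvement within each group.
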